Criteria for Withholding and/or Permanent Discontinuation of Amgen Investigational Product and Other Protocol-required Therapies Due to Potential Hepatotoxicity	66
Criteria for Rechallenge of Amgen Investigational Product and Other Protocol-required Therapies After Potential Hepatotoxicity	67
Drug-induced Liver Injury Reporting and Additional	00
Assessments	
List of Tables	
	10
Table 2-1. Schedule of Activities	
Table 7-1. Study Treatments	
Table 12-1. Analyte Listing	40
Table 12-2. Conditions for Withholding and/or Permanent Discontinuation of Amgen Investigational Product and Other Protocol-required Therapies Due to Potential Hepatotoxicity	67
List of Figures	
Figure 2-1. Study Schema	9
Figure 12-1. Sample Electronic Serious Adverse Event Contingency Form	55
Figure 12-2. Pregnancy and Lactation Notification Worksheet	62

Page 6 of 70

Date: 16 August 2017 **Page 7 of 70**

1. Protocol Synopsis

Protocol Title: A Multicenter, Open-label, Single-arm, Study to Evaluate Safety and Tolerability of Repatha in Patients with Homozygous Familial Hypercholesterolemia (HoFH) in India

Short Protocol Title: An Open-label Study to Characterize Safety and Tolerability of Repatha in Homozygous Familial Hypercholesterolemia in India

Study Phase: 4

Indication: Homozygous Familial Hypercholesterolemia (HoFH)

Rationale

In March 2017, Repatha® (evolocumab) was approved in India as prescription medication in combination with other lipid-lowering therapies for adults and adolescents aged 12 years and over with HoFH. This non-comparative, interventional phase 4 study is designed to fulfil the postmarketing requirement to assess safety and tolerability of Repatha in Indian HoFH subjects when administered under the locally approved label.

Objective(s)/Endpoint(s)

Objectives	Endpoints			
Primary				
To characterize the safety and tolerability in homozygous familial hypercholesterolemia HoFH patients in India exposed to 12 weeks of Repatha	The subject incidence of treatment-emergent adverse events			
Secondary				
To characterize the efficacy of 12 weeks of Repatha on low-density lipoprotein cholesterol (LDL-C), apolipoprotein B (ApoB) and lipoprotein(a) [Lp(a)] in HoFH patients in India	 Percent change from baseline in LDL-C at week 12 Percent change from baseline in ApoB at week 12 Percent change from baseline in Lp(a) at week 12 			

Hypotheses

This phase 4 study is descriptive in nature, describing safety and tolerability of Repatha in subjects with HoFH in India.

Overall Design

This open-label, multicenter, non-comparative phase 4 study of Repatha is part of Amgen's postmarketing requirement to the Indian Regulatory Authority. The study population consists of approximately 30 Indian subjects with HoFH and for whom Repatha is indicated in accordance with the approved prescribing information in India.

The assignment of subjects to protocol treatment will be decided by the investigator according to inclusion/exclusion criteria and laboratory assessments at screening (including fasting lipids). Subjects who are enrolled will be instructed to continue to

Date: 16 August 2017 **Page 8 of 70**

follow a diet limiting saturated fat to less than 7% of total daily calories and will be required to maintain their current lipid-lowering drug therapy throughout the duration of the trial.

Number of Subjects

Approximately 30 subjects with HoFH will be enrolled in the study.

Summary of Subject Eligibility Criteria

Key inclusion criteria include subjects 12 to 80 years of age with a clinical diagnosis of HoFH who are on a stable, low-fat diet, and taking pre-existing lipid-lowering therapies. Key exclusion criteria include use of mipomersen or lomitapide within 6 months of screening and has previously received evolocumab or any other proprotein convertase subtilisin/kexin type 9 (PCSK9)-inhibiting therapy.

For a full list of eligibility criteria, please refer to Section 6.1 to Section 6.2.

Treatments

Subjects will receive Repatha 420 mg once monthly (QM) subcutaneous (SC) and study visits will occur approximately every 4 weeks (the week 4 study visit is optional: subjects can either self-administer at home or visit study site and study staff will administer Repatha). For subjects on apheresis, they may receive Repatha 420 mg SC every 2 weeks to correspond with their apheresis schedule (the week 2 and week 6 study visits are optional: subjects can either self-administer at home or visit study site and study staff will administer Repatha). Final administration of Repatha will occur at week 8. The end of study (EOS) visit and the last estimation of lipids will occur at week 12 for all subjects. Subjects will be encouraged to complete all planned visits, study procedures, and measurements until the end of the study regardless of their adherence to Repatha administration.

Procedures

Informed consent must be obtained before starting any screening procedure. The following procedures will occur per the Schedule of Activities: physical examination, physical measurements, demographics, medical history, vital signs, dietary advice, adverse event assessment, concomitant therapies review, laboratory assessments, Tanner staging (for subjects < 18 years old only), and Repatha administration.

For a full list of study procedures, including the timing of each procedure, please refer to Section 9.2 and the Schedule of Activities in Table 2-1.

Statistical Considerations

Approximately 30 subjects with HoFH will be enrolled in this study. The primary analysis set is the full analysis set (FAS), which includes all enrolled subjects who have received at least 1 dose of Repatha. Unless specified otherwise, the FAS will be the default analysis set in this study.

The final analysis will be performed at the end of the study (defined as when the last subject enrolled has completed the safety follow-up/EOS visit).

For a full description of statistical analysis methods, please refer to Section 10.

Sponsor Name: Amgen Inc.

[figure not shown]

Protocol Number: 20170199
Date: 16 August 2017
Page 9 of 70

2. Study Schema and Schedule of Activities

2.1 Study Schema

Figure 2-1. Study Schema

IP = investigational product; QM = once monthly; SC = subcutaneous ^a For subjects on apheresis only.

AMGEN®

Protocol Number: 20170199

Date: 16 August 2017 **Page 10 of 70**

2.2 Schedule of Activities

Product: Evolocumab

Table 2-1. Schedule of Activities

	Screening		Treat	ment P	eriod		Follow-up	
Procedure	(up to 4 weeks before day 1)	W1 (day 1)	W2ª	W4 ^b	W6ª	W8	W12 ^c	Notes
General and Safety Assessments	3							
Informed consent	Х							
Inclusion and exclusion criteria	×							Includes specific eCRFs for lactation status and HoFH clinical criteria
Demographics	Х							
Physical examination	Х	Х					Х	
Physical measurements: weight	Х							
Medical history	Х							
Vital signs (BP, HR)	Х	Х				Х	Х	
Dietary advice	Х							
AE/SAE/ADE/DRE	Х	Х	Xd	Xd	Xd	Х	Х	
Concomitant therapies review	Х	Х	Xd	Xd	Xd	Х	Х	
Tanner staging ^e	Х						Х	
Laboratory Assessments ^f	Laboratory Assessments ^f							
Urine and/or serum pregnancy test (females of childbearing potential only)	Х						х	Additional on-treatment pregnancy testing may be performed at the investigator's discretion if there is suspicion that a female subject is pregnant or per local laws and regulations.

Abbreviations and footnotes defined on last page of table.

Protocol Number: 20170199

Date: 16 August 2017 **Page 11 of 70**

Table 2-1. Schedule of Activities

	Screening		Treat	ment P	eriod		Follow-up	
Procedure	(up to 4 weeks before day 1)		W2 ^a	W4 ^b	W6ª	W8	W12 ^c	Notes
Laboratory Assessments ^f (contin	ued)							
Hematology	Х							
Chemistry	Х							
Fasting lipids, ApoA1, ApoB	Х	Х				Х	Х	
Lp(a)	Х	Х				X	Х	
Urinalysis	Х							
Pharmacogenetics samples (optional)		Х						
Study Treatment								
Amgen investigational product		Х	Xa	Х	Xa	Х		Administration at weeks 2 and 6 are for subjects on apheresis only.

Page 2 of 2

ADE = adverse device effect; AE = adverse event; Apo = apolipoprotein; BP = blood pressure; DRE = disease-related events; eCRF = electronic case report form; EOS = end of study; FCBP = female of childbearing potential; HoFH = homozygous familial hypercholesterolemia; HR = heart rate; Lp(a) = lipoprotein (a); SAE = serious adverse event; W = Week

^a Subjects on apheresis only: may initiate treatment with 420 mg every 2 weeks to correspond with their apheresis schedule. On weeks 2 and 6, subjects can self-administer Repatha at home, no site visit required. However, if the subject prefers, they can visit study site and study staff will administer Repatha.

^b For all subjects: on week 4, subjects can self-administer Repatha at home, no site visit required. However, if the subject prefers, they can visit study site and study staff will administer Repatha.

^c The EOS visit will occur at week 12 (4 weeks after last dose of Repatha).

^d Will call if subject chooses to administer Repatha at home.

e In pediatric subjects 12 to 17 years of age (includes the year after the subject completes the 17th year after birth but not the day of completing the 18th year after birth).

f Subjects will fast for 9 hours and abstain from strenuous exercise for 72 hours before each blood collection for clinical laboratory tests.

Date: 16 August 2017 **Page 12 of 70**

3. Introduction

3.1 Study Rationale

In March 2017, Repatha® (evolocumab) was approved in India as prescription medication in combination with other lipid-lowering therapies for adults and adolescents aged 12 years and over with homozygous familial hypercholesterolemia (HoFH). This non-comparative, interventional phase 4 study is designed to fulfil the postmarketing requirement to assess safety and tolerability of Repatha in Indian HoFH subjects when administered under the locally approved label.

3.2 Background

3.2.1 Disease

Homozygous familial (most commonly referred to as HoFH) is a rare genetic disorder occurring in approximately 1:1 000 000 individuals. Many of these represent compound heterozygotes possessing different mutations on each of the low-density lipoprotein receptor (LDLR) alleles (Goldstein et al, 2001). The geographical prevalence and characterization of the specific LDLR mutations among homozygous patients though often well known in western population; is not so well characterized in India. The incidence of major cardiovascular illness among homozygous individuals is higher than that of affected familial hypercholesterolemia heterozygotes, with events such as myocardial infarction happening by the second decade of life (Goldstein et al, 2001). Due to the rapid and aggressive nature of atherosclerosis in HoFH, it is commonly studied and treated as a disease beginning in childhood and manifesting with untoward morbidity and mortality in affected adults. This also applies to other, even more rare genetic causes of dyslipidemia that fall under the umbrella diagnosis of familial hypercholesterolemia. These conditions include mutations in proprotein convertase subtilisin/kexin type 9 (PCSK9; dominant-gain of function), apolipoprotein B (ApoB; dominant-loss of function) and autonomic recessive hypercholesterolemia (ARF; recessive-loss of function). High-dose statin therapy has reduced both low-density lipoprotein cholesterol (LDL-C) (in the range of 10% to 25%) as well as cardiovascular event rates among patients with HoFH (Neil et al, 2008; Raal et al, 1997). However, the response to therapy has been limited in part by the biology underlying this disease, and possibly by the concomitant elevation of PCSK9 levels that result from statin treatment (Lakoski et al, 2009). In addition to maximal medical therapy, some patients have been placed on a biweekly to weekly schedule of lipid apheresis, a process similar to hemodialysis where LDL-C is physically removed from their circulation. Though a

Date: 16 August 2017 **Page 13 of 70**

helpful tool in the treatment of HoFH, this invasive procedure is cumbersome, expensive, and not readily available in India.

HoFH LDL receptor mutation results in impaired LDL receptor function and impaired LDL-C clearance. The response variability is based on LDL receptor functionality according to the genetic defect associated with the LDL receptor activities even between subjects confirmed as HoFH. Therapies supporting LDL-C clearance through LDL-C receptor function, like Repatha, can be expected to further reduce LDL-C with existing pharmacologic therapies. Repatha in addition to lipid-lowering therapies in HoFH subjects, shown to have a safety profile response and being effective and well-tolerated (Raal et al, 2014).

3.2.2 Amgen Investigational Product Background: Repatha

Repatha (evolocumab) is a full human monoclonal IgG2 directed against human PCSK9. Repatha binds to PCSK9 and inhibits circulating PCSK9 from binding to the LDLR, preventing PCSK9-mediated LDLR degradation and permitting LDLR to recycle back to the liver cell surface. By inhibiting the binding of PCSK9 to LDLR, Repatha increases the number of LDLRs available to clear LDL from the blood, thereby lowering LDL-C levels. Following single subcutaneous (SC) administration of 140 mg or 420 mg of Repatha, maximum suppression of circulating unbound PCSK9 occurred by 4 hours. Unbound PCSK9 concentrations returned toward baseline when Repatha concentrations decreased below the limit of quantitation. Repatha has been found to be effective in reducing LDL-C levels in patients with HoFH in the TESLA study. This study was a multicenter, double-blind, randomized, placebo-controlled, 12-week trial in 49 patients with HoFH. In this trial, 33 patients received SC injections of 420 mg of Repatha once monthly (QM) and 16 patients received placebo as an adjunct to other lipid-lowering therapies (eg. statins, ezetimibe). The mean age at baseline was 31 years, 49% were women, 90% White, 4% were Asian, and 6% other. The trial included 10 adolescents (ages 13 to 17 years), 7 of whom received Repatha. The mean LDL-C at baseline was 349 mg/dL with all patients on statins (atorvastatin or rosuvastatin) and 92% on ezetimibe. In these patients with HoFH, the difference between Repatha and placebo in mean percent change in LDL-C from baseline to week 12 was -31% (95% CI: -44%, -18%; p < 0.0001) (Raal et al, 2014).

A detailed description of the chemistry, pharmacology, efficacy, and safety of Repatha is provided in the Investigator's Brochure.

Date: 16 August 2017 **Page 14 of 70**

4. Objectives, Endpoints, and Hypotheses

4.1 Objectives and Endpoints

Objectives	Endpoints		
Primary			
To characterize the safety and tolerability in homozygous familial hypercholesterolemia HoFH patients in India exposed to 12 weeks of Repatha.	The subject incidence of treatment- emergent adverse events		
Secondary			
To characterize the efficacy of 12 weeks of Repatha on low-density lipoprotein cholesterol (LDL-C), apolipoprotein B (ApoB) and lipoprotein(a) [Lp(a)] in HoFH patients in India	 Percent change from baseline in LDL-C at week 12 Percent change from baseline in ApoB at week 12 Percent change from baseline in Lp(a) at week 12 		

4.2 Hypotheses

This phase 4 study is descriptive in nature, describing safety and tolerability of Repatha in subjects with HoFH in India.

5. Study Design

5.1 Overall Design

This open-label, multicenter, non-comparative phase 4 study of Repatha is part of Amgen's post-marketing requirement to the Indian Regulatory Authority. The study population consists of approximately 30 Indian subjects with HoFH and for whom Repatha is indicated in accordance with the approved prescribing information in India.

The assignment of subjects to protocol treatment will be decided by the investigator according to inclusion/exclusion criteria and laboratory assessments at screening (including fasting lipids). Subjects who are enrolled will be instructed to continue to follow a diet limiting saturated fat to less than 7% of total daily calories (lyengar et al, 2016) and will be required to maintain their current lipid-lowering drug therapy throughout the duration of the trial. Subjects will receive Repatha 420 mg QM SC and study visits will occur approximately every 4 weeks (the week 4 study visit is optional: subjects can either self-administer at home or visit study site and study staff will administer Repatha). For subjects on apheresis, they may receive Repatha 420 mg SC every 2 weeks to correspond with their apheresis schedule (the week 2 and week 6

Protocol Number: 20170199

Date: 16 August 2017 **Page 15 of 70**

study visits are optional: subjects can either self-administer at home or visit study site and study staff will administer Repatha). If the subject chooses to self-administer Repatha at home during the optional site visits, the staff will call the subject to collect any adverse events or changes in concomitant medication. Final administration of Repatha (for all subjects) will occur at week 8. The end of study (EOS) visit and the last estimation of lipids will occur at week 12 for all subjects. The following procedures will occur per the Schedule of Activities: physical examination, physical measurements, demographics, medical history, vital signs, dietary advice, adverse event assessment, concomitant therapies review, laboratory assessments, Tanner staging (for subjects < 18 years old only), and Repatha administration (see Table 2-1). Subjects will be encouraged to complete all planned visits, study procedures, and measurements until the end of the study regardless of their adherence to Repatha administration.

The overall study design is described by a study schema in Section 2.1. The endpoints are defined in Section 4.1.

5.2 Number of Subjects

Approximately 30 subjects with HoFH will be enrolled in the study.

Subjects in this clinical investigation shall be referred to as "subjects". For the sample size justification, see Section 10.1.

5.2.1 Replacement of Subjects

Subjects who are withdrawn or removed from treatment or the study will not be replaced.

5.2.2 Number of Sites

Approximately 15 investigative sites in India will be included in the study. Sites that do not enroll subjects within 3 months of site initiation may be closed.

5.3 End of Study

5.3.1 End of Study Definition

Primary Completion: The primary completion date is defined as the date when the last subject is assessed or receives an intervention for the final collection of data for the primary endpoint(s), for the purposes of conducting the primary analysis, whether the study concluded as planned in the protocol or was terminated early.

The primary completion date is the date when the last subject has completed the assessments for week 12.

If the study concludes prior to the primary completion date originally planned in the protocol (ie, early termination of the study), then the primary completion will be the date

Protocol Number: 20170199

Date: 16 August 2017 **Page 16 of 70**

when the last subject is assessed or receives an intervention for evaluation in the study (ie, last subject last visit).

End of Study: The EOS date is defined as the date when the last subject across all sites is assessed or receives an intervention for evaluation in the study (ie, last subject last visit), following any additional parts in the study (eg, safety follow-up), as applicable.

5.3.2 Study Duration for Subjects

After signing the informed consent, the subject should be enrolled within 4 weeks. Including the screening period, the investigational product administration dates (weeks 1, 4, and 8 [and weeks 2 and 6 for subjects on apheresis]), and an EOS visit that occurs at week 12 (4 weeks after last dose of investigational product), the total duration of study participation for a subject will be up to approximately 16 weeks.

5.4 Justification for Investigational Product Dose

The Repatha dose being used in this study is in accordance with the terms of its marketing authorization in India. The dose for this study is 420 mg given QM SC for 8 weeks. For subjects on apheresis, they may initiate treatment with 420 mg SC every 2 weeks to correspond with their apheresis schedule.

Repatha will be administered at 140 mg in 1.0 mL (3 administrations by prefilled autoinjector/pen [Al/pen]) for a total of 3.0 mL (420 mg evolocumab) administered. The SC injections should be administered in a consecutive fashion with all injections completed within 30 minutes.

5.5 Patient Input on Study Design

Not applicable.

6. Study Population

Investigators will be expected to maintain a screening log of all potential study candidates that includes limited information about the potential candidate (eg, date of screening). This log may be completed and updated via an Interactive Voice/Web Response System (IxRS).

Eligibility criteria will be evaluated during screening.

Before any study-specific activities/procedures, the appropriate written informed consent must be obtained (see Appendix 3).

Prospective approval of protocol deviations to recruitment and enrollment criteria, also known as protocol waivers or exemptions will not be provided.

Date: 16 August 2017 **Page 17 of 70**

6.1 Inclusion Criteria

Subjects are eligible to be included in the study only if all of the following criteria apply:

If the subject is ≥ 18 years of age, the subject has provided informed consent prior to initiation of any study specific activities/procedures. If the subject is
 18 years of age, the subject's legally acceptable representative has provided informed consent

- 102 Male or female \geq 12 to \leq 80 years of age at the time of signing the informed consent
- 103 Clinical diagnosis of HoFH based on a history of an untreated LDL-C concentration greater than 500 mg/dL (13 mmol/L) together with either xanthoma before 10 years of age or evidence of familial hypercholesterolemia in both parents
- On a stable, low-fat diet and taking pre-existing lipid-lowering therapies (such as statins, cholesterol-absorption inhibitors, bile-acid sequestrants or nicotinic acid, or combinations thereof) with no plan to change medication or dosage within 4 weeks of screening and during the time frame of the trial, with fasting central laboratory LDL-C concentration > 130 mg/dL (3.4 mmol/L) at screening
- 105 Fasting triglycerides ≤ 400 mg/dL (4.5 mmol/L) by central laboratory at screening

6.2 Exclusion Criteria

Subjects are excluded from the study if any of the following criteria apply.

- 201 Use of mipomersen or lomitapide within 6 months of screening.
- 202 Known active infection or major hematologic, renal, metabolic, gastrointestinal, hepatic, or endocrine dysfunction.
- Currently receiving treatment in another investigational device or drug study, or less than 30 days since ending treatment on another investigational device or drug study(ies). Other investigational procedures while participating in this study are excluded.
- Female subject is pregnant or breastfeeding or planning to become pregnant or breastfeed during treatment and for an additional 15 weeks after the last dose of Repatha. (Females of childbearing potential should only be included in the study after a confirmed menstrual period and a negative highly sensitive urine or serum pregnancy test).
- Female subjects of childbearing potential unwilling to use **an** acceptable method of effective contraception during treatment and for an additional 15 weeks after the last dose of Repatha. Refer to Appendix 5 for additional contraceptive information.
- Subject has known sensitivity to any of the products to be administered during dosing.
- 207 History or evidence of any other clinically significant disorder, condition or disease (with the exception of those outlined above) that, in the opinion of the investigator or Amgen physician, if consulted, would pose a risk to subject safety or interfere with the study evaluation, procedures or completion.

Protocol Number: 20170199

Date: 16 August 2017 **Page 18 of 70**

Subject has previously received evolocumab or any other PCSK9-inhibiting therapy.

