6.3 Subject Enrollment

Before subjects begin participation in any study-specific activities/procedures, Amgen requires a copy of the site's written institutional review board/independent ethics committee (IRB/IEC) approval of the protocol, informed consent form, and all other subject information and/or recruitment material, if applicable (see Appendix 3).

The subject or the subject's legally acceptable representative must personally sign and date the IRB/IEC and Amgen approved informed consent before commencement of study-specific procedures.

A subject is considered enrolled when the investigator decides that the subject has met all eligibility criteria. The investigator is to document this decision and date, in the subject's medical record and in/on the enrollment electronic case report form (eCRF).

Each subject who enters into the screening period for the study (up to 4 weeks before enrollment) receives a unique subject identification number before any study-related activities/procedures are performed. The subject identification number will be assigned IxRS. This number will be used to identify the subject throughout the clinical study and must be used on all study documentation related to that subject.

The subject identification number must remain constant throughout the entire clinical study; it must not be changed after initial assignment, including if a subject is rescreened.

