9.2.4.1 Pregnancy Testing

A high sensitive (urine or serum) pregnancy test should be completed at screening for females of childbearing potential.

Note: Females who have undergone a bilateral tubal ligation/occlusion should have pregnancy testing per protocol requirements. (If a female subject, or the partner of a male subject, becomes pregnant it must be reported on the Pregnancy Notification Worksheet, see Figure 12-2). Refer to Appendix 5 for contraceptive requirements.

A pregnancy test should be performed at week 12/EOS after discontinuing protocolrequired therapies.

Additional on-treatment pregnancy testing may be performed at the investigator's discretion or as required per local laws and regulations.

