Appendix 5. Contraceptive Guidance and Collection of Pregnancy and Lactation Information

Study-specific contraception requirements for adult female subjects of childbearing potential or for pediatric subjects who have reached puberty are outlined in Section 6.2.

Adult female subjects of childbearing potential or for pediatric studies who have reached puberty must receive pregnancy prevention counseling and be advised of the risk to the fetus if they become pregnant during treatment and for 15 weeks after the last dose of protocol-required therapies.

Definition of Females of Childbearing Potential

A female is considered fertile following menarche and until becoming postmenopausal unless permanently sterile. Permanent sterilization methods include hysterectomy, bilateral salpingectomy, and bilateral oophorectomy.

Females in the following categories are not considered female of childbearing potential:

- premenopausal female with 1 of the following:
 - documented hysterectomy;
 - documented bilateral salpingectomy; or
 - documented bilateral oophorectomy.

Note: Site personnel documentation from the following sources is acceptable:

- 1) review of subject's medical records; 2) subject's medical examination; or
- 3) subject's medical history interview.
- premenarchal female
- postmenopausal female
 - A postmenopausal state is defined as no menses for 12 months without an alternative medical cause. A high follicle stimulating hormone (FSH) level in the postmenopausal range may be used to confirm a postmenopausal state in women not using hormonal contraception or hormonal replacement therapy (HRT). However, in the absence of 12 months of amenorrhea, a single FSH measurement is insufficient.
 - Females on HRT and whose menopausal status is in doubt will be required to use 1 of the non-hormonal highly effective contraception methods if they wish to continue their HRT during the study. Otherwise, they must discontinue HRT to allow confirmation of postmenopausal status before study enrollment.

Contraception Methods for Female Subjects

Acceptable Methods of Effective Contraception

 combined (estrogen and progestogen containing) or progestogen-only hormonal methods given via oral, intravaginal, transdermal, injectable, or implantable route)

Date: 16 August 2017 Page 59 of 70

- intrauterine device (IUD)
- intrauterine hormonal-releasing system (IUS)
- bilateral tubal ligation/occlusion

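### Exclusion 204 (pregnancy) is verified before dosing by one scheduled test up to 4 weeks before day 1, with no required re-check before the first dose

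*Protocol*

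**What the plan says.** **Criterion.** Exclusion 204 (Protocol 6.2) excludes women who are pregnant. Women able to conceive "should only be included in the study after a confirmed menstrual period and a negative highly sensitive urine or serum pregnancy test". No time limit relative to the first dose is set for either the period or the test.

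**When it is checked.** The opening of Section 6 says "Eligibility criteria will be evaluated during screening", and Table 2-1 marks the inclusion/exclusion row at screening only. Section 9.2.4.1 says that a highly sensitive "pregnancy test should be completed at screening for females of childbearing potential", with a second test at week 12/EOS. The pregnancy test row of Table 2-1 agrees: one mark at screening, one at week 12, none on day 1 or at weeks 2 to 8.

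**How early screening may be.** The screening column of Table 2-1 reads "up to 4 weeks before day 1". Section 9.1.2 defines day 1 as the date of the first dose. Section 6.3 counts the same 4 weeks back from enrollment, which it defines as the investigator's eligibility decision.

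**Contraception and counselling.** Exclusion 205 concerns women unwilling to use an "acceptable method of effective contraception during treatment and for an additional 15 weeks after the last dose of Repatha". Appendix 5 requires that they "be advised of the risk to the fetus if they become pregnant during treatment" and for 15 weeks after the last dose.

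**Other testing.** Table 2-1 allows extra on-treatment tests at the investigator's discretion on suspicion of pregnancy, or under local law. Section 9.2.4.1 allows them at discretion without naming suspicion. Appendix 2 allows additional tests at any time that the investigator finds necessary.

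**The concern.** A criterion that bars pregnant women protects them only if it is true when the drug is given. Here it is verified at screening, and nothing in the schedule requires it to be verified again before the first dose. The contraception and counselling texts begin with treatment, so they are silent on the same interval. A conception between the screening test and day 1 would leave the woman meeting exclusion 204 at her first dose, with no required procedure to reveal it.

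What is at stake is subject safety and the verification of eligibility. Safety and tolerability are the only primary objective (Protocol 4.1), and the protocol itself treats exposure in pregnancy as a matter for exclusion, counselling, discontinuation and 24-hour reporting (8.1, Appendix 5). The statistical results are not at risk.

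**Working it through.** The plan gives no figure to reproduce, so the check is a comparison of passages plus calendar arithmetic.

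**Inputs**
- Earliest screening: 4 weeks before day 1 (Table 2-1).
- Day 1: first dose (9.1.2).
- Week 12: target study day 85 (SAP Appendix A).
- Doses: weeks 1, 4 and 8, plus weeks 2 and 6 for subjects on apheresis (5.3.2).
- Visit window: ± 7 days for on-study visits (9.1.2).

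**Arithmetic**
- Screening test to first dose: 4 × 7 = 28 days at most.
- First dose to next scheduled test: 85 − 1 = 84 days.
- Between the two scheduled tests: 28 + 84 = 112 days (16 weeks) at most, or 112 + 7 = 119 days if the visit window applies to week 12.
- Doses scheduled between the tests: 3, or 5 with apheresis.

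**What is required in the interval from screening test to first dose**

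| Possible safeguard | Where | Required before the first dose? |
|---|---|---|
| Repeat pregnancy test | Table 2-1, 9.2.4.1 | No |
| Repeat eligibility check | Table 2-1, Section 6 | No |
| Stated contraception period | Exclusion 205 | Not mentioned |
| Fetal-risk counselling period | Appendix 5 | Not mentioned |
| Extra testing | Table 2-1, 9.2.4.1, Appendix 2 | Allowed, not required |
| Day 1 physical examination | Table 2-1, 9.2.1.4 | Yes, but it is not a pregnancy test |

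**After the first dose.** The week 4 dose may be given at home with a telephone call in place of a visit, as may the week 2 and week 6 doses for subjects on apheresis (5.1, Table 2-1). Some women may therefore not be seen on site between day 1 and week 8. A pregnancy ends study treatment (8.1, Appendix 5), but only once it is known.

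**How many women.** The protocol does not say. If the 49% women in the earlier 12-week HoFH trial (3.2.2) applied here, 0.49 × 30 = 14.7, or about 15 women. That is an assumption, and it is an upper limit for those of childbearing potential, because subjects may be 12 to 80 years old (6.1). The documents give neither the share without contraception in the interval nor a chance of conception, so the calculation stops there.

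**The case against.** The strongest case on the other side is that, on the test schedule, the documents agree with one another. Section 9.2.4.1 matches Table 2-1, and exclusion 205 matches Appendix 5. On this view the point is only a preference for a stricter schedule. Four weeks is also a maximum. Exclusion 204 removes women planning pregnancy during treatment, and exclusion 205 removes those unwilling to use contraception. An investigator may test at any time, including on day 1. Details of product safety are left to the Investigator's Brochure, so fetal risk cannot be weighed from these documents.

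Much of this stands, and it limits the size of the point. It does not close the gap: every safeguard named is optional, begins with treatment, or depends on intention, whereas an unplanned and unrecognised conception depends on none of them.

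Four stronger readings are tempting and should be resisted.
- **That such a woman would receive every dose before anyone knew.** She could. But staff contact her at week 4 and see her at week 8, and suspicion is a named reason to test.
- **That the gap can exceed 4 weeks because 6.3 counts back from enrollment.** Table 2-1 ties screening to day 1, and 5.3.2 gives about 16 weeks in total, which is 4 + 12. Section 6.3 is a wording mismatch.
- **That dosing her breaches the rule against waivers in Section 6.** That rule bars advance approval of deviations from entry criteria. A conception after a valid negative test is not a waiver.
- **That a probability can be put on it.** No document supports the inputs.

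**Conclusion.** The point holds as an inexpensive safety improvement. For up to 28 days before the first dose, no pregnancy test is required and no contraception period is stated. A conception in that interval could lead to dosing of a woman who meets exclusion 204, unless pregnancy is suspected or the investigator chooses to test. The next scheduled test comes 84 days after the first dose at target dates, after the last of the 3 or 5 doses.

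The number affected is likely small and cannot be computed from the documents. The 28 days assume the earliest screening that Table 2-1 allows; a site that screens later has a shorter interval. The conclusion rests on what the schedule requires, not on any assumed conception rate, and it does not bear on the descriptive analyses.

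**What to change.** 1. In Table 2-1 and Section 9.2.4.1, add a day 1 pregnancy test for females of childbearing potential, with a negative result recorded before the first dose. The local urine test already listed in Table 12-1 serves.
2. In Table 2-1, mark the inclusion/exclusion row at day 1 as a pre-dose check.
3. Ask the sponsor to reconcile the period stated in exclusion 205 and Appendix 5 with the interval from the screening test to the first dose. When contraception or counselling should begin is a clinical decision for the sponsor.
4. Align the 4-week wording in Section 6.3 (before enrollment) with Table 2-1 (before day 1).

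The cost is a short amendment and one urine dipstick per woman of childbearing potential. No visit is added, because the day 1 dose is already given on site (7.6). The downside is an occasional late screen failure on day 1, which is what the criterion intends.
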